1.0 Synopsis of Study Design Procedures

This study is a prospective, randomized, placebo-controlled, multicenter study to evaluate the efficacy and safety of amifampridine phosphate in subjects diagnosed with Lambert Eaton Myasthenic Syndrome (LEMS). The endpoint assessments of this Phase 3 study are as follows:

- Primary:
 - To assess the clinical efficacy of amifampridine phosphate compared with placebo in adults with LEMS, based on change of the co-primary endpoints Quantitative Myasthenia Gravis (QMG) Score and Subject Global Impression (SGI).
- Secondary:
 - Clinical Global Impression of Improvement (CGI-I)
- Exploratory:
 - Greater than 20% increase in the average time of 3 repetitions for Timed Up and Go test (3TUG)
 - Subject rating on change of most bothersome symptom for them.

1.1 Design and Treatment

Subjects will be randomized on Day 0 to either treatment group in a 1:1 ratio. Investigational product (IP) will be administered under double-blind conditions such that neither the Investigator nor subject knows if they are taking placebo or amifampridine phosphate.

Amifampridine phosphate (at the subject's optimal dose established prior to enrollment into this trial) or placebo will be dispensed by the site pharmacist, according to the randomization schedule, to begin with the next dose after all Day 0 assessments are completed and continued for 4 days. Although subjects at the high (dose \geq 60 mg/day) and low (dose < 60 mg/day) are randomized separately, the study is not powered to detect differences across dose levels and no inferential analyses are planned to compare dose levels (See Section 1.3). The amifampridine phosphate dose is 30 mg to 80 mg total daily dose (expressed as freebase form), given in 3 to 4 divided doses, with no single dose >20 mg.

1.2 Study Procedures

The planned duration of participation for each subject is 5 days (Day 0 through Day 4), excluding the screening period, which can last up to 7 days. Those subjects satisfying all inclusion and exclusion criteria will be randomized to a Treatment Group on the last day of the screening period (Day 0). The treatment period will take place on the remainder of Day 0 and Days 1 through 4. The following assessments will be performed at the beginning and end of the 4-day treatment period:

- Vital signs
- Urine sample for amifampridine level (collected at days 3, and 4)
- Clinical Global Impression of Improvement (CGI-I)
- Subject Global Impression (SGI)
- Quantitative Myasthenia Gravis (QMG)
- Triple Timed Up and Go (3TUG)
- Patient most bothersome symptom question
- Record concomitant medications
- Monitor for adverse events (throughout the 5-day treatment period)

1.3 Sample Size

The study is powered with respect to the co-primary efficacy endpoints of the study. For change from baseline (CFB) in QMG Scores, a between-treatment difference of -3.5 and a standard deviation of at most 3, a sample size of at least 24 subjects will provide power of at least 80% for a 0.05 level two-sided test. Similarly, for CFB in SGI Scores, a between-treatment difference of -2.1 and a standard deviation of at most 2, a sample size of at least 26 subjects will provide power of 80% for a 0.05 level two-sided test. Thus a total sample size of 26 subjects, equally randomized to two treatment sequences, will provide power of at least 80% for each of the two co-primary endpoints.

The randomization is stratified by high and low dose of the investigational product. Due to the fact that each dose strata has an insufficient number of observations to be adequately powered to do meaningful hypothesis testing, no statistical comparisons by treatment will be done for individual dose-strata subgroups.

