6.4.2 Efficacy of Amifampridine in LEMS

A Phase 3, randomized, double-blind, placebo-controlled study (LMS-002) evaluated the efficacy and safety of amifampridine tablets 10 mg, as amifampridine phosphate (30-80 mg

Page 25

total daily dose) versus placebo in patients with LEMS. The 38 patients treated with amifampridine phosphate had statistically significant improvement in both primary efficacy measures relative to patients treated with placebo. The change in QMG scores from baseline (Day 1, Part 2) to Day 14 (Part 3) reached statistical significance (p=0.0452), with the least square (LS) mean for QMG score increasing by 2.2 in placebo-treated patients, and increasing by 0.4 in amifampridine-treated patients. For the other primary endpoint, subject global impression (SGI), patients who were receiving amifampridine on Day 1 reported, on average, that they were "pleased" (SGI score of 5.9 ± 1.2) with the test medication while they were receiving it. After being switched to placebo tablets, their opinions dropped, on average, 2.7 ± 2.3 points. The LS mean was -2.6 for the placebo group and -0.8 for the amifampridine group, a difference of 1.8 ± 0.6 (p=0.0028), corresponding to a patient assessment, of "mixed" for the placebo tablets. This substantial change in patients' assessments, to a worsening of their condition while receiving placebo, was considered clinically significant.

In addition to Study LMS-002, 5 randomized, double-blind, placebo-controlled studies and 1 double-blind study with an active comparator (reported in abstract form only) in 71 patients with LEMS are reported in the clinical literature. In all 6 studies, amifampridine (in base form) was shown to be more effective for the symptomatic treatment of LEMS compared with placebo or active comparator across a number of independent measures of neurological function. Supportive data from multiple published uncontrolled investigations and case reports demonstrate the long-term benefits of treatment with amifampridine in patients with LEMS, and show that removal of patients from drug has led to recurrence of underlying symptoms. Refer to the Firdapse Investigator Brochure (February, 2015) for further details on these studies.

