13 STATISTICAL METHODS AND DETERMINATION OF SAMPLE SIZE

13.1 Determination of Sample Size

For Change From Baseline in QMG Scores, a between-treatment difference of -3.5 and a standard deviation at most 3, a sample size of at least 24 patients will provide power of at least 80% for a 0.05 level test. Similarly, for Change From Baseline in SGI Scores, a between-treatment difference of -2.1 and a standard deviation at most 2, a sample size of at least 26 patients will provide power of 80% for a 0.05 level test. Thus a total sample size of 26 patients, equally randomized to two treatment sequences, will provide power of at least 80% for each of the two co-primary endpoints.

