2.0 Data Analysis Considerations

2.1 Types of Analyses

Analyses will consist of summarizing efficacy and safety data. Unless otherwise stated, two-sided P values <0.05 will be considered as statistically significant.

The following standards will be applied for the analyses unless otherwise specified. Simple summary statistics (descriptive statistics) for continuous data are: n (number of non-missing observations), mean, median, standard deviation, minimum, and maximum. The frequency count and percentage will be used to summarize categorical data. Summary statistics will be presented by treatment. All data collected will be presented in the by-subject data listings, sorted by subject and by time point, where appropriate.

Additionally, the randomization is stratified by high and low dose of the investigational product. Therefore, descriptive statistics, grouped by both

treatment and dose level strata, will be presented using the same descriptive analyses described above for continuous and categorical data, as applicable.

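### At the plan's own inputs, 26 patients give about 81% power for QMG but only 73% for SGI, and about 59% to 71% for both together; the closing power claim should be restated.

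*SAP*

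**What the plan says.** SAP 1.3 begins "The study is powered with respect to the co-primary efficacy endpoints of the study" and then treats the endpoints one at a time.

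- QMG: "a between-treatment difference of -3.5 and a standard deviation of at most 3", for which "a sample size of at least 24 subjects will provide power of at least 80% for a 0.05 level two-sided test".
- SGI: "a between-treatment difference of -2.1 and a standard deviation of at most 2", for which "a sample size of at least 26 subjects will provide power of 80% for a 0.05 level two-sided test".

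It concludes that 26 in total, split equally, gives 80% or more for each endpoint. Protocol 13.1 and the synopsis use the same inputs and reach the same conclusion, without the word two-sided in the sample-size paragraph. Planned enrolment is about 28 (synopsis and protocol 8.1).

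The significance rule in SAP 2.1 is that "two-sided P values <0.05 will be considered as statistically significant". SAP 4.2.1 applies one such test to each co-primary with no split of alpha. The primary objective (protocol 7.1) joins SGI and QMG with the word and. No section gives a joint power, a correlation between the endpoints, or an explicit rule for declaring the trial positive.

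**The concern.** There are two separate faults. First, the SGI statement does not follow from its inputs: at 26 patients a two-sided 0.05 test has less than 80% power. Second, power for each endpoint is offered as the support for calling a two-co-primary study powered. When two endpoints must both reach significance, the probability of success is the joint probability. That cannot exceed the lower of the two powers, and it falls short of that unless the endpoints move together almost perfectly.

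At stake is how the design is judged and how a result is read. A reader of the current text would put the chance of a positive trial near 80%, assuming the planned effects are real. The inputs support a figure some 10 to 20 points lower, so a miss on one endpoint would be less surprising than the plan suggests.

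**Working it through.** **Inputs.** QMG difference 3.5, SD 3; SGI difference 2.1, SD 2 (SAP 1.3). Two-sided alpha 0.05 (SAP 1.3 and 2.1). Allocation 1:1, so n = 13 per arm at 26 and n = 14 at 28. The correlation between endpoints is not given, so 0 to 0.9 is taken as an assumption.

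**Step 1: reproduce the stated sample sizes (normal approximation).** Total N = 4 × [SD × (1.960 + 0.842) / difference]².

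- QMG: 4 × (3 × 2.802 / 3.5)² = 23.1, so 24. This reproduces.
- SGI: 4 × (2 × 2.802 / 2.1)² = 28.5, so 30. The plan's 26 does not reproduce.

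**Step 2: power per endpoint (noncentral t).** Noncentrality = difference / [SD × √(2/n)], with 2n − 2 degrees of freedom. At n = 13 the critical value is 2.064.

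- QMG: 3.5 / (3 × √(2/13)) = 2.974; power 81.4%.
- SGI: 2.1 / (2 × √(2/13)) = 2.677; power 72.9%.

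The normal approximation gives 84.5% and 76.3%, so SGI falls short either way. At n = 14 the t-test powers are 84.4% and 76.2%. SGI needs 16 per arm (32 in total) by t to reach 80%.

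**Step 3: joint power.** At correlation 0 it is the product: 0.814 × 0.729 = 0.593. For other correlations I simulated bivariate normal changes and applied both t-tests (200,000 runs per setting).

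| Correlation | 26 patients | 28 patients | Exactly 80% for each endpoint |
|---|---|---|---|
| 0 | 59% | 64% | 64% |
| 0.5 | 64% | 69% | 69% |
| 0.9 | 71% | 74% | 75% |

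The last column isolates the joint-success effect: 0.8 × 0.8 = 0.64 at correlation 0, and the bivariate normal probability otherwise. The first two columns combine that effect with the SGI shortfall.

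**Step 4: sensitivity scenario only.** Protocol 6.4.2 reports LMS-002 "with the least square (LS) mean for QMG score increasing by 2.2 in placebo-treated patients, and increasing by 0.4 in amifampridine-treated patients", a difference of 2.2 − 0.4 = 1.8, and an SGI difference of 1.8. With the plan's SDs and 13 per arm, QMG power is 31% and SGI power 60%. Joint power is 0.312 × 0.596 = 19% at correlation 0, rising to 31% at 0.9.

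**The case against.** **The plan claims 80% for each endpoint, not for the trial.** This is correct. A reader might infer that the plan states an 80% chance of overall success; no sentence does. The joint figure is missing rather than misstated. The SGI figure, however, is a stated number that its own inputs do not support.

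**No passage says that both endpoints must succeed.** Also correct. The rule is inferred from the term co-primary, the wording of the objective, and the full 0.05 used for each test. The inference is reasonable, because if either endpoint sufficed the type I error would be 1 − 0.95² = 9.75% for independent tests. The plan should still state the rule.

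**The SDs are upper limits and the model adjusts for baseline.** Both could raise power. SGI reaches 80% at 13 per arm by t if the SD is about 1.83 or less, or if baseline SGI correlates with change at about 0.4. But the plan states its power at the upper limit and cites no baseline correlation. Neither route brings joint power to 80% merely by lifting SGI to 80%, as the last column of the table shows.

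**A stronger reading from LMS-002.** The QMG assumption, "For Change From Baseline in QMG Scores, a between-treatment difference of -3.5 and a standard deviation at most 3", is 3.5 / 1.8 = 1.94 times the difference in protocol 6.4.2. A reader might infer that QMG is more likely to fail than succeed. The documents do not support going that far. LMS-002 was read out at Day 14, whereas this trial replaces a stable dose and reads out at Day 4. Superseded sample-size text in the amendment log (protocol Appendix 6) also attributes a QMG difference of about 2.8 to that study, so 1.8 is not the only QMG figure in the documents. At 2.8 with SD 3, QMG power at 13 per arm is about 63%. What stands is that the current text gives no source for 3.5.

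**Conclusion.** The point holds as a correction to the stated power. At the plan's own inputs with 26 patients, QMG has about 81% and SGI about 73%, so at least 80% for each is not delivered. If success requires both, joint power is about 59% to 71%, or 64% to 74% at 28 patients. No correlation from 0 to 0.9 brings it to 80%.

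These figures rest on an unadjusted two-sample t-test, SDs at their stated upper limits, no loss of patients, and a both-must-succeed rule that is implied rather than written. The correlation range is an assumption. The validity of the planned analysis is not in question. The LMS-002 calculation is one scenario, not a forecast.

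**What to change.** Keep the sample size. In SAP 1.3, protocol 13.1 and the synopsis, replace the closing claim with text along these lines: with 13 per arm and a two-sided 0.05 t-test, power is about 81% for QMG and 73% for SGI; the trial succeeds only if both are significant; the probability of this is about 59%, 64% and 71% at correlations of 0, 0.5 and 0.9 between the endpoints, and about 64%, 69% and 74% with 28 patients. If the sponsor relies on a smaller SD or on baseline adjustment, the value used should be stated.

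Optionally, add the LMS-002 differences as a labelled sensitivity scenario (QMG about 31%, joint about 19% to 31% at 26 patients), noting the Day 14 readout.

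The cost is one paragraph in three places and a less favourable published figure. No endpoint, test, analysis set or enrolment target changes.

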Patients will be randomized (1:1 ratio) on the last day of the screening period (Day 0) to either amifampridine phosphate or placebo. Beginning with the next dose after all Day 0 assessments are completed, the patient will take, under double-blind conditions, either amifampridine phosphate tablets or placebo tablets through Day 4, with a clinic visit on the last day (Day 4) for assessments (Table 3). Any unused portion of dispensed drug will be returned.

During all phases of the study, safety and efficacy assessments will be made as detailed in the Schedule of Assessments in Table 3.

NUMBER OF PATIENTS PLANNED:

Approximately 28 patients to enroll in the study.

Page 5

CRITERIA FOR INCLUSION AND EXCLUSION:

Individuals eligible to participate in this study must meet all of the following inclusion criteria:

- 1. Male or female ≥18 years of age with LEMS and currently receiving a stable dose of amifampridine phosphate for at least 7 days.
- 2. Diagnosis of LEMS by antibody testing or EMG.
- 3. Completion of anti-cancer treatment at least 3 months (90 days) prior to Screening.
- 4. If receiving peripherally acting cholinesterase inhibitors (e.g. pyridostigmine), a stable dose of cholinesterase inhibitors is required for at least 7 days prior to randomization and throughout the study.
- 5. If receiving permitted oral immunosuppressants (prednisone or other corticosteroid), a stable dose is required for at least 30 days prior to randomization and throughout the study.
- 6 Female patients of childbearing potential must practice an effective, reliable contraceptive regimen during the study.
- 7. Able to perform all study procedures and assessments.
- 8. Willing and able to travel to study site and attend all clinic study visits.
- 9. Willing and able to provide written informed consent.

Individuals who meet any of the following exclusion criteria are not eligible to participate in the study:

- 1. Clinically significant long QTc interval on ECG in previous 12 months.
- 2. Seizure disorder.
- 3. Active brain metastases.
- 4. Unable to ambulate.
- 5. Pregnant or lactating females.
- 6. Any other condition which, in the opinion of the Investigator, might interfere with the patient's participation in the study or confound the assessment of the patient.
- 7. Patients who cannot discontinue immunomodulatory treatment (e.g. mycophenolate, azathioprine, cyclosporine) within 3 weeks before screening.

INVESTIGATIONAL PRODUCT(S), DOSE, ROUTE, AND REGIMEN:

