The investigational product (IP) is amifampridine phosphate tablets 10 mg, and it will be provided in round, white-scored tablets, containing amifampridine phosphate formulated to be the equivalent of 10 mg amifampridine base per tablet. The total daily dose will be individually determined by the Investigator, within the bounds of a total daily dose of up to 80 mg, divided into doses taken 3 to 4 times per day as prescribed by the Investigator, based on optimal neuromuscular benefit.

Amifampridine phosphate tablets are to be taken orally by mouth.

Page 6

The investigational product, and matching placebo, will be provided by Catalyst Pharmaceuticals, Inc., [name].

REFERENCE THERAPY, DOSE, ROUTE, AND REGIMEN:

The reference therapy is a placebo, provided as tablets indistinguishable from amifampridine tablets. The placebo will be administered consistent with the dose and dose regimen of the investigational product (amifampridine phosphate).

CRITERIA FOR EVALUATION:

Safety:

Safety will be assessed by the incidence of treatment-emergent adverse events (TEAEs), including serious adverse events (SAEs). Vital signs, physical examination, and concomitant medications will also be evaluated.

Efficacy:

- Primary:
 - To assess the clinical efficacy of amifampridine phosphate compared with placebo in individuals with LEMS, based on change of the co-primary endpoints QMG Score and Subject Global Improvement (SGI).
- Secondary:
 - Clinical Global Impression of Improvement (CGI-I)
- Exploratory:
 - Greater than 20% increase in the average time of 3 repetitions for Timed Up and Go test (3TUG)
 - o Patient rating on change of most bothersome symptom for them.

STATISTICAL METHODS:

Sample Size Determination

For Change From Baseline in QMG Scores, a between-treatment difference of -3.5 and a standard deviation at most 3, a sample size of 24 patients will provide power of at least 80% for a 0.05 level test. Similarly, for Change From Baseline in SGI Scores, a between-treatment difference of -2.1 and a standard deviation at most 2, a sample size of 26 patients will provide power of 80% for a 0.05 level test. Thus a total sample size of 26 patients, equally randomized to the two treatments, will provide power of at least 80% for each of the two co-primary endpoints.

Safety Analysis

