8.1 Overall Study Design and Plan

This randomized (1:1), double-blind, placebo-controlled, parallel-group study is designed to evaluate the efficacy and safety of amifampridine phosphate in patients diagnosed with LEMS. Patients will have been receiving unblinded drug treatment in the expanded access program (EAP-001), after which blinded treatment effect will be assessed for continuation or cessation of drug. The study is planned to include approximately 28 male and female patients. The planned duration of participation for each patient is 5 days, excluding the screening period, which can last up to 7 days.

Those patients successfully satisfying all screening criteria will be randomized to a treatment group. Amifampridine phosphate (at the patient's optimal dose) or placebo will be dispensed by the site pharmacist, according to the randomization schedule, to begin with the next dose after all Day 0 assessments are completed and continued for 4 days. After completion of the study, patients will be eligible for expanded access treatment program with open-label amifampridine phosphate. Since patients will have been out of the expanded accesss program for less than 30 days, as LMS-003 participants, rescreening to return to expanded access program will not be required, per the protocol, and patients may immediately resume their participation in the expanded access program (EAP-001).

Page 29

Screening

Patients receiving amifampridine phosphate treatment for LEMS, and meeting the inclusion and exclusion criteria are eligible to participate in this study. They can be randomized if on stable dose and frequency of amifampridine phosphate for at least 1 week before being randomized to a treatment. Screening and randomization (Day 0) may be combined into a single visit.

Treatment (Days 1-4) (+1 day)

Patients will be randomized (1:1 ratio) on the last day of the screening period (Day 0) to either amifampridine phosphate or placebo. Beginning with the next dose after all Day 0 assessments are completed, the patient will take, under double-blind conditions, either amifampridine phosphate tablets or placebo tablets through Day 4, with a clinic visit on the last day (Day 4) for assessments (Table 3). Any unused portion of dispensed drug will be returned to the pharmacy.

During the study, safety and efficacy assessments will be made as detailed in the Schedule of Assessments in Table 3.

Table 3. Schedule of Assessments

	Samaaning	Randomization	Days 1-4

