13.4 Efficacy Analysis

Efficacy analyses will be conducted on the FAS and PP populations, with the FAS population serving as the primary analysis set. For each efficacy variable with a corresponding assessment at Baseline, Change From Baseline (CFB) will be computed as the post-treatment result minus the Baseline result. The post-treatment result will be the result obtained on Day 4, unless the subject discontinued treatment early, in which case the post-treatment result may be obtained at an earlier time point. For statistical tests, two-sided P values <0.05 will be considered as statistically significant.

Summary statistics for QMG score and the corresponding CFB will be presented by treatment. The analysis of CFB for Total QMG Score is a coprimary efficacy endpoint and analysis will be performed by fitting a fixed effects linear model to the data with CFB as the response. The model will include terms for treatment and QMG at Baseline. The following test comparing the least squares (LS) means will be conducted to evaluate the treatment effect:

HA,0: LSMeanQMG(A) = LSMeanQMG(P) vs. HA,1: $LSMeanQMG(A) \neq LSMeanQMG(P)$,

where LSMeanQMG(A) is the QMG LS mean of the amifampridine treatment group and LSMeanQMG(P) is the QMG LS mean of the placebo treatment group.

The raw scores and CFB for each item of QMG will be summarized by treatment. Between-treatment comparisons with respect to CFB for Right arm outstretched, Left arm outstretched, Right leg outstretched, and Left leg outstretched will be performed using a GLM with terms for treatment, QMG at Baseline and treatment duration (in days).

Page 54

Summary statistics for SGI score and the corresponding CFB will be presented by treatment. The analysis of CFB for SGI is a coprimary efficacy endpoint and analysis will be performed by fitting a fixed effects linear model to the data with CFB as the response. The model will include terms for treatment and SGI at Baseline. The following test comparing the LS means will be conducted to evaluate the treatment effect:

HB,0: LSMeanSGI(A) = LSMeanSGI(P) vs. HB,1: LSMeanSGI(A) \neq LSMeanSGI(P),

where LSMeanSGI(A) is the SGI LS mean of the amifampridine treatment group and LSMeanSGI(P) is the SGI LS mean of the placebo treatment group.

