4.2 Analysis of Efficacy Variables

4.2.1 Primary Efficacy Analysis

Primary efficacy analyses will be conducted on the FAS and PP populations, with the FAS population serving as the primary analysis set. For both primary efficacy variables, change from baseline (CFB) will be computed as the post-treatment result (Day 4) minus the Baseline result (Day 0). The post-treatment result will be the result obtained on Day 4, unless the subject discontinued treatment early, in which case the post-treatment result may be obtained at an earlier time point.

Summary statistics for the QMG Day 0 assessment, QMG Day 4 assessment, and the corresponding CFB will be presented by treatment. The analysis of CFB for Total QMG Score is a co-primary efficacy endpoint and analysis will be performed by fitting a fixed effects linear model to the data with CFB as the response. The model will include terms for treatment and QMG at Baseline. The following test comparing the least squares (LS) means will be conducted to evaluate the treatment effect:

H_{A,0}: LSMeanQMG(A) = LSMeanQMG(P) vs. H_{A,1}: LSMeanQMG(A) \neq LSMeanQMG(P),

where LSMeanQMG(A) is the QMG LS mean of the amifampridine treatment group and LSMeanQMG(P) is the QMG LS mean of the placebo treatment group.

The raw individual QMG scores (each individual QMG domain) for Day 0, Day 4, and CFB will be summarized by treatment and dose within treatment. Additional between-treatment comparisons for several of the individual QMG domains, and the sum of these domains, will be performed using a fixed effects linear model as an exploratory endpoint. No inferential procedures will be performed on the other QMG domains. See section 4.2.2 for details.

Summary statistics for SGI score and the corresponding CFB will be presented by treatment. The analysis of CFB for SGI is a co-primary efficacy endpoint and analysis will be performed by fitting a fixed effects linear model to the data with CFB as the response. The model will include terms for treatment and SGI at Baseline. The following test comparing the LS means will be conducted to evaluate the treatment effect:

 $H_{B,0}$: LSMeanSGI(A) = LSMeanSGI(P) vs. $H_{B,1}$: LSMeanSGI(A) \neq LSMeanSGI(P),

where LSMeanSGI(A) is the SGI LS mean of the amifampridine treatment group and LSMeanSGI(P) is the SGI LS mean of the placebo treatment group.

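### At the stated inputs, 26 patients give about 73% power for co-primary SGI (76% by normal approximation), not 80%

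*SAP*

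**What the plan says.** SAP 1.3 takes a between-treatment difference of 2.1 (written as -2.1) in SGI change from baseline and an SD of at most 2, and states that "a sample size of at least 26 subjects will provide power of 80% for a 0.05 level two-sided test". With the QMG inputs (difference 3.5, SD at most 3, at least 24 patients), it concludes that a total of 26, equally randomized, "will provide power of at least 80% for each of the two co-primary endpoints".

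The protocol repeats the SGI figure. Section 13.1 has "a sample size of at least 26 patients will provide power of 80% for a 0.05 level test" and the synopsis has "a sample size of 26 patients will provide power of 80% for a 0.05 level test". Neither sentence gives the sidedness, but Protocol 13.4 does: "two-sided P values <0.05 will be considered as statistically significant".

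Planned enrolment is slightly larger than 26. The synopsis has "Approximately 28 patients to enroll in the study", and Protocol 8.1 has "The study is planned to include approximately 28 male and female patients".

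For the SGI analysis, SAP 4.2.1 specifies: "The model will include terms for treatment and SGI at Baseline". None of the sample-size texts names a formula, a residual SD or a baseline correlation.

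**The concern.** SGI is one of two co-primary endpoints and, on the plan's own inputs, the one with the smaller standardised difference (2.1/2 = 1.05, against 3.5/3 = 1.167 for QMG). A standardised difference of 1.05 with 13 per arm looks too small for 80% power at two-sided 0.05.

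If the figure is wrong, so is the conclusion drawn from it for both co-primary endpoints. The plan then understates the chance of missing a true SGI difference of 2.1, which it implies is 20%. This concerns a planning statement only: no analysis, estimate or type I error rate depends on it.

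**Working it through.** **Inputs.** SGI difference 2.1 and SD 2, the stated upper bound (SAP 1.3). Two-sided alpha 0.05 (SAP 1.3, Protocol 13.4). 1:1 allocation (SAP 1.1). Parallel groups (Protocol 8.1). A total of 26, so n = 13 per arm (SAP 1.3), and about 28, so n = 14 per arm (synopsis, Protocol 8.1).

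**Formulas.** Noncentrality: δ = (difference/SD) × √(n/2).
- Normal approximation: power = Φ(δ − 1.960).
- t-test: power from the noncentral t distribution with 2n − 2 df and noncentrality δ.

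**Attempt to reproduce the SGI figure at 26.** δ = 1.05 × √(13/2) = 2.677.
- Normal: Φ(2.677 − 1.960) = Φ(0.717) = 76.3%.
- t-test, 24 df, critical value 2.064: 72.9%. Taking one df off for the baseline covariate, with SD still 2, gives 72.7%.

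The stated 80% is not reproduced by either method.

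**Results by sample size**

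| Total N | SGI, t-test | SGI, normal | QMG, t-test | QMG, normal |
|---|---|---|---|---|
| 24 | 69.1% | 73.0% | 78.0% | 81.5% |
| 26 | 72.9% | 76.3% | 81.4% | 84.5% |
| 28 | 76.2% | 79.3% | 84.4% | 87.0% |
| 30 | 79.3% | 82.0% | 86.9% | 89.2% |
| 32 | 82.0% | 84.4% | 89.1% | 91.0% |

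**Sample size for 80%, SGI.** The normal formula gives n per arm = 2 × (2/2.1)² × (1.960 + 0.842)² = 14.2, so 15 per arm and 30 in total. By t-test it is 16 per arm, 32 in total.

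**Do both stated sample sizes come from one method?** For QMG the normal formula gives 2 × (3/3.5)² × (1.960 + 0.842)² = 11.5, so 12 per arm and 24 in total, as stated. The t-test gives only 78.0% at 24. The QMG figure therefore fits the normal approximation, but that same method gives 30 for SGI, not 26. Neither method reproduces both figures.

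**Other readings.**
- One-sided 0.05 at 26 gives 83.0% (t-test) or 84.9% (normal), but the SAP says two-sided.
- Taking 26 as the size of each arm gives 96.0% (t-test), but the SAP gives 26 as the total.

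**What would make 80% true?**
- At SD 2, the SGI difference detectable with 80% power by t-test is 2.29 at 26 and 2.20 at 28.
- At a difference of 2.1, allowing 2n − 3 df for the covariate, the residual SD must be at most 1.83 at 26 or 1.91 at 28.
- If the SD of 2 is the unadjusted SD of change (the documents do not say), this needs a correlation r between baseline SGI and its change of √(1 − (1.830/2)²) = 0.40 at 26 or √(1 − (1.906/2)²) = 0.30 at 28. Over an assumed range for r, power at 26 is 74.4% at r = 0.2, 76.7% at 0.3, 79.9% at 0.4 and 84.1% at 0.5.

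**The case against.** Four points can be made for the plan.

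- **The t-test may not be the planners' method.** The QMG figure of 24 suggests the normal approximation. The SGI shortfall is then 3.7 points at 26 and only 0.7 points at the planned 28. This is fair, and both methods should be reported, but neither gives 80% at 26, which is the number the plan states.

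- **The SD is an upper bound, so power may be higher.** That is possible, but a bound means the statement has to hold at SD 2, and there it fails.

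- **The primary model adjusts for baseline SGI, and the earlier trial hints at a smaller residual SD.** This is the strongest point. Protocol 6.4.2 reports an LMS-002 SGI difference of 1.8 ± 0.6 (p=0.0028). Assume that 0.6 is a standard error and that 38 patients were split 19/19. The residual SD is then 0.6/√(2/19) = 1.85 from the standard error, or about 1.73 from the p-value. For a difference of 2.1, power at 26 would be about 79% or 84%. However, the standard error and the split are assumptions, and the sample-size text does not use this result. The same section also gives a smaller effect, 1.8, with which power at 26 would be about 66% or 72%. It reports a spread of 2.3 for the change in patients switched to placebo. This evidence might support a revised justification, but it does not establish the 80% as written.

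- **Only wording is at stake.** This is true: about 28 patients are planned, drop-outs may be replaced (Protocol 8.2.4), and no analysis changes. It limits how much the error matters, but the stated figure is still wrong.

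**Conclusion.** The concern holds. At the stated difference of 2.1 and SD bound of 2, two-sided 0.05, SGI power at 26 patients is 72.9% (t-test) or 76.3% (normal), which is 7.1 or 3.7 points below the stated 80%. At 28 the shortfall is 3.8 or 0.7 points. The chance of missing a true difference of 2.1 at 26 is 27% or 24%, against the implied 20%.

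The conclusion that 26 patients suffice for both co-primary endpoints fails for SGI only, because QMG reaches 80% at 26 by either method.

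These figures take the SD of 2 at face value, with no gain from baseline adjustment and no loss of patients. A smaller residual SD could restore 80%, but the plan neither states nor justifies one.

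**What to change.** Amend SAP 1.3, Protocol 13.1 and the synopsis in one of two ways.

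1. **Restate the power.** Give SGI as about 73% at 26 and 76% at 28 (t-test, SD 2), or about 76% and 79% by normal approximation. Give QMG as about 81% and 84% (t-test). Name the method, and limit the claim of at least 80% to QMG. If the t-test is the named method, the QMG sentence about 24 patients also needs correcting, since it gives 78.0% there.
2. **Keep 80% for SGI and justify it.** State that the calculation uses the residual SD after baseline adjustment, at most 1.83 at 26 or 1.91 at 28, and give the evidence for that SD.

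In the same edit, the sign of the SGI difference could be aligned with that of QMG, because benefit raises SGI and lowers QMG; this does not affect two-sided power. Joint power for both endpoints could be added, with its assumed correlation stated, but this is optional.

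The cost is wording in three places and, under the first option, a less favourable stated power for SGI. It needs no extra patients and no change to any analysis.
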